3.2.3 Rationale for Patient Population

IPF is a heterogeneous disease with variable progression characterized by deterioration of lung function. There is no established method of combining clinical or biomarker measures to accurately determine prognosis or define the stage of disease; therefore, the inclusion criteria have been set to include a broad population of patients with IPF. The study will target patients with a confirmed diagnosis of IPF consistent with the

diagnostic criteria published in the recent international ATS/ERS/JRS/ALAT guidelines (Raghu et al. 2011). Consistent with these guidelines, HRCT will be required to confirm the diagnosis of IPF and to exclude other possible causes of ILD in patients considered for enrolment. Surgical lung biopsies are not required for eligibility; however, those patients who have undergone such a procedure will have their slides adjudicated by central review to confirm eligibility in accordance with ATS/ERS/JRS/ALAT guidelines.

The inclusion criteria for this Phase II study were selected to allow patients with a broad spectrum of IPF disease the opportunity to participate, as reflected in the lung function (% FVC $\geq 40\%$ and $\leq 100\%$, % DL_{CO} $\geq 25\%$ and $\leq 90\%$), exercise capacity (6MWT ≥ 100 meters), and the length of time with disease (IPF diagnosis within previous 5 years of screening Visit 1) entry criteria. These parameters have been proposed to characterize disease severity and to identify patients who are likely to be influenced by the study intervention.

The primary objective of Study GB28547 is to evaluate lebrikizumab as monotherapy or in combination with pirfenidone background therapy compared with placebo in a Phase II study in patients with a confirmed diagnosis of IPF. Two cohorts of patients will be studied; **Cohort A** (patients with no IPF background medications) and **Cohort B** (patients who were treated with pirfenidone as background medication throughout the study period).

Eligibility in **Cohort A** excludes current use of pirfenidone and other approved, investigational, or other widely used therapies for IPF because of the potential confounding effects these therapies may have on the efficacy and safety analysis of lebrikizumab monotherapy. During the open-label lebrikizumab period, at the investigator's discretion, a patient can start background therapy, including use of pirfenidone or other treatment, provided that it is a therapy for IPF *approved* in the applicable region (e.g., European Union, Canada, Mexico, Peru, or Japan) (see Section 4.4.1.2).

Eligibility for **Cohort B** requires that all patients be on a maximum tolerated dose of pirfenidone ≤ 2403 mg/day as standard background therapy. A minimum of 4 weeks of exposure to pirfenidone is required prior to randomization, anticipating 52 weeks of background therapy. No other therapies may be used to treat IPF (see Section 4.4.1.2).

The Principal Investigator should notify the Medical Monitor of proposed changes in concomitant IPF therapy prior to starting rescue therapy *throughout the study for patients in either Cohort A or Cohort B*.

3.2.4 Rationale for Primary and Disease Response-Based Endpoints

In natural history settings of IPF, it is widely accepted that a decline in absolute FVC of 10% or more is a surrogate marker of mortality (Raghu et al. 2011), and in the absence

of an alternative explanation, disease progression. Smaller (5%–10%) but progressive, sustained declines in FVC may also represent disease progression ([Zappala et al. 2010](#)).

Changes over time in a patient's FVC (whether analyzed continuously or categorically above/below a threshold value) have been correlated with survival time in multiple large cohorts of patients with IPF ([Collard et al. 2007](#); [Flaherty et al. 2003](#); [du Bois 2011](#)).

Furthermore, the FDA approvals of pirfenidone and nintedanib were based upon similar measures of FVC: the change in percentage of predicted forced vital capacity (%FVC) from baseline to 52 weeks for pirfenidone and annual rate of decline in FVC. Patients treated with pirfenidone had a 4.5% treatment benefit relative to placebo treated patients and a modest improvement in survival (HR (95% HR [95% CI] = 0.75 [0.51-1.11]) (pirfenidone FDA label). Similar outcomes were observed in the OFEV trials (NEJM 2014 and product label).

The primary endpoint of this Phase II study will be the absolute change from baseline to Week 52 (end of treatment) in percentage of predicted FVC.

A key secondary endpoint in this study is PFS, which is defined as the time from study treatment randomization to the first occurrence of any one of the following events:

- Death from any cause
- Non-elective hospitalization for any cause
- Decrease from baseline of $\geq 10\%$ in FVC (L) (relative change)

The most clinically relevant domain of the proposed PFS endpoint is all-cause mortality ([du Bois 2010](#); [Papiris et al. 2012](#); [Raghu et al. 2012](#)). It is well defined, reliable, and easy to measure. All-cause mortality avoids losing clinically relevant information and inducing informative bias that occurs when deaths related to the study intervention are misclassified as “unrelated” and are censored. The all-cause mortality endpoint also captures potential off-target effects that could impact risk of mortality ([Raghu et al. 2012](#)).

Although it is commonly reported that the median survival time of those diagnosed with IPF is 3 to 5 years ([Cottin 2012](#)), the individual clinical course can be highly variable and unpredictable. In recent clinical trials the mortality rate in the placebo arms is consistently low highlighting that events of death are relatively rare in IPF trials ([Wells et al. 2012](#)). The current design combines all-cause mortality with additional parameters that have been shown to correlate with survival to increase the overall event rate.

The second PFS component, non-elective all-cause hospitalization, has validity in capturing disease progression leading to a decrease in patient health. Hospitalizations for those with IPF are often significant clinical events that carry a poor prognosis. The majority of hospitalizations in this population are respiratory related and correlates to cause of death, which is usually due to progressive fibrosis rather than

commonly occurring comorbidities (Martinez et al. 2005; Ley et al. 2011). Limitations of hospitalization endpoints include a variety of non-disease-related factors that can influence whether hospitalization occurs, such as access to health care, social support, and regional practice patterns, as well as the challenge of clinical data retrieval when a patient is hospitalized at a facility outside the study. Despite these limitations, non-elective hospitalization remains a clinically meaningful endpoint (Raghu et al. 2011). Similar to all-cause mortality, the all-cause hospitalization endpoint also captures potential off-target effects that could impact risk of hospitalization.

As stated above, it is widely accepted that a decline of 10% in a patient's FVC is a sign of disease progression and therefore a useful prognostic factor (Raghu et al. 2011). Using a relative (rather than absolute) change in FVC maximizes the chance of identifying a $\geq 10\%$ decline without sacrificing prognostic accuracy (Richeldi et al. 2011). Categorical decline of $\geq 10\%$ in FVC (relative) is the third PFS component.

3.2.5 Rationale for Control Group

A placebo-treated control group will be used in Cohort A of this study and a pirfenidone+placebo-treated control group will be used in Cohort B to assess the differences in pulmonary function, PFS, IPF-specific health-related quality of life, and safety in patients who receive lebrikizumab compared with patients who receive placebo. The use of a control group is necessary given the variability in the clinical course seen with different IPF cohorts in other clinical studies. Patients in the control group will undergo the same study assessments as the lebrikizumab-treated patients.

During the placebo-controlled periods, N-acetylcysteine or IPF therapy approved by local regulatory authorities can be initiated only after a confirmed progression event ($\geq 10\%$ decrease in FVC or non-elective hospitalization). No other therapies for IPF can be started at any time during the study.

For patients assigned to Cohort B, other approved therapies may be initiated in the absence of disease progression if pirfenidone is stopped because of safety considerations (see Section 4.4.1.2).

3.2.6 Rationale for Biomarker Assessments

The study will include a significant exploratory component focused on identification of biomarkers that may be prognostic for patients likely to have an accelerated rate of disease progression or diagnostic for identifying patients likely to benefit from treatment with lebrikizumab. Periostin is an IL-13-inducible protein with a serum level that correlates with benefit from treatment with lebrikizumab in patients with asthma (Woodruff et al. 2007; Corren et al. 2011). Periostin is also elevated in the serum of patients with IPF, and these levels have been shown to be negatively correlated with pulmonary function parameters (FVC and DL_{CO}) over a 6-month period (Okamoto et al. 2011; Naik et al. 2012). Periostin has been proposed to be a pathogenic factor in IPF on the basis of reduced bleomycin-induced pulmonary fibrosis observed

in periostin-deficient mice, suggesting an additional mechanism by which IL-13 may contribute to disease (Uchida et al. 2012).

Serum levels of periostin appear to have a distribution in patients with IPF similar to what has been observed in patients with asthma. Patients will be stratified across each treatment arm on the basis of periostin levels, tertiary to region, and baseline FVC. Patients with baseline periostin ≥ 50 ng/mL will be considered periostin high, and patients with baseline periostin < 50 ng/mL will be considered periostin low (Corren et al. 2011).

Serum and plasma samples will be collected during screening, at baseline and throughout the study, and at unscheduled visits to assess the relationship between periostin and other IL-13- and IPF-related biomarkers, disease progression, clinical status, and treatment benefit. Other IL-13- and IPF-related biomarkers that will be investigated may include but are not limited to CCL18, YKL40, COMP, OPN, CCL17, and CCL13. If novel IL-13- or IPF-related biomarkers are identified, they may be measured from stored serum or plasma.

3.3 OUTCOME MEASURES

3.3.1 Efficacy Outcome Measures

3.3.1.1 Primary Efficacy Outcome Measure

The primary efficacy outcome measure for this study is the *annualized rate of decrease in percentage of predicted FVC over 52 weeks (% FVC/year)*.

3.3.1.2 Secondary Efficacy Outcome Measures

The secondary efficacy outcome measures for this study are as follows:

- *Annualized rate of decline in 6MWT distance over 52 weeks*
- *Time from randomization to first occurrence of a $\geq 10\%$ absolute decline in percentage of predicted FVC or death from any cause*
- *Annualized rate of decrease in percentage of predicted DL_{CO} over 52 weeks*
- PFS, defined as the time from study treatment randomization to the first occurrence of any of the following *disease progression or death* events:
 - Death from any cause
 - All-cause hospitalization
 - A decrease from baseline (*relative change*) of $\geq 10\%$ in FVC (mL/year)
- *Annualized rate of decrease in FVC over a 52-week period (mL/year)*
- *Annualized rate of decrease in ATAQ-IPF total score over a 52-week period (see Appendix 5 for a description of the instrument)*
- *Time from randomization to first occurrence of the SGRQ (see Appendix 5 for a description of the questionnaire) worsening (total score) as defined by reaching MID (Swigris et al. 2010): Total Score = 7 or death from any cause*

- Time from randomization to non-elective hospitalization *or death from any cause*
- Time from randomization to first event of acute IPF exacerbation *as defined below:*

IPF exacerbation is defined as an event that meets all of the following criteria as determined by the investigator:

Unexplained worsening or development of dyspnea within the previous 30 days

***And** radiologic evidence of new bilateral ground-glass abnormality or consolidation superimposed on a reticular or honeycomb background pattern that is consistent with UIP*

***And** absence of alternative causes, such as left heart failure, pulmonary embolism, pulmonary infection (on the basis of endotracheal aspirate or bronchoalveolar lavage, if available, or investigator judgment), or other events leading to acute lung injury (e.g., sepsis, aspiration, trauma, reperfusion pulmonary edema)*

3.3.2 Safety Outcome Measures

All safety outcome measures will be assessed by comparing results from the lebrikizumab treatment group with the placebo group. The safety outcome measures for this study are as follows:

- Frequency of adverse events during the study
- Severity of adverse events during the study
- Incidence of anti-therapeutic antibodies (ATAs) against lebrikizumab throughout the study

3.3.3 Pharmacokinetic Outcome Measures

The PK outcome measures for this study are as follows:

- Serum lebrikizumab concentration at Week 52 (C_{wk52})
- Predose serum lebrikizumab concentrations (C_{min}) at Weeks 4, 12, 24, and 36 ($C_{min,Wk4}$, $C_{min,Wk12}$, $C_{min,Wk24}$, and $C_{min,Wk36}$)
- Elimination half-life of lebrikizumab

3.3.4 Exploratory Outcome Measures

The exploratory outcome measures for this study include the following:

- Change from baseline to Week 52 in radiographic findings on pulmonary HRCT, including QLF score
- *Change from screening (corresponding to timing for randomization strata) in serum and plasma biomarkers (e.g., periostin and CCL18) and change from baseline in serum and plasma biomarkers (e.g., periostin, CCL18, YKL40, COMP, OPN, CCL13)*
- Serum lebrikizumab concentrations during the extended treatment and the 14-week safety follow-up period

- Exposure-response relationships (to be evaluated as warranted)
- Change from baseline to Week 52 in the Borg CR10 Scale
- *Change from baseline to Week 52 in the ATAQ-IPF*
- *Time from randomization to first occurrence of SGRQ individual domain worsening as defined by reaching MID (Swigris et al. 2010): Symptom =8, Activity =5, Impact =7, or death from any cause*
- *Change from baseline to Week 52 in the SGRQ*

The analysis plan for the exploratory HRCT and biomarkers will be specified in a separate document.

4. MATERIALS AND METHODS

4.1 PATIENTS

Approximately 480 patients ≥ 40 years of age who have a diagnosis of IPF *are* enrolled in this study.

4.1.1 Inclusion Criteria

Patients must meet the following criteria for study entry:

- Able and willing to provide written informed consent and to comply with the study protocol
- Age ≥ 40 years at Visit 1
- Have a diagnosis of IPF based on the ATS/ERS/JRS/ALAT consensus statement on IPF (Raghu et al. 2011) within the previous 5 years from time of screening and confirmed at baseline
- Have a central review assessment of an HRCT performed during the screening period or within 12 months prior to the start of screening.

All patients who have undergone an SLB as part of their initial workup should have pathology slides sent in for SLB central review assessment.

Eligibility will be determined on the basis of assessments in [Table 1](#).

- A Multidisciplinary Discussion of Diagnosis (MDD) based on 2011 ATS/ERS/JRS/ALAT guidelines will be utilized to finalize the diagnosis in the event the initial central review outcome results for HRCT and SLB are disparate (inconsistent with UIP/definite UIP).

Table 1 Combined High-Resolution Computed Tomography and Surgical Lung Biopsy Eligibility Assessment

HRCT Assessment	Surgical Lung Biopsy Assessment					
	Definite UIP	Probable UIP	Possible UIP	Non-Classifiable Fibrosis	Inconsistent with UIP	No SLB
Definite UIP	Eligible	Eligible	Eligible	Eligible	Not eligible	Eligible
Possible UIP	Eligible	Eligible	Eligible	Eligible	Not eligible	Eligible
Inconsistent with UIP	May be eligible/MDD	Not eligible	Not eligible	Not eligible	Not eligible	Not eligible

HRCT = high-resolution computed tomography; MDD = Multidisciplinary Discussion of Diagnosis; SLB = surgical lung biopsy; UIP = usual interstitial pneumonia.

Additionally, patients must meet the following criteria for study entry:

- FVC $\geq 40\%$ and $\leq 100\%$ of predicted at screening
- Stable baseline lung function as evidenced by a difference of $< 10\%$ in FVC (L) measurements between screening and Day 1, Visit 2 prior to randomization
- DL_{CO} $\geq 25\%$ and $\leq 90\%$ of predicted at screening
- Ability to walk ≥ 100 meters unassisted in 6 minutes
- Cohort A: No background IPF therapy for ≥ 4 weeks allowed prior to randomization and throughout the placebo-controlled study period
- Cohort B: Tolerated dose of pirfenidone ≤ 2403 mg/QD for ≥ 4 weeks required prior to randomization and throughout the placebo-controlled study period

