4.3.4 Pirfenidone Background Treatment

The recommended dose of pirfenidone is 2403 mg/d (or 1800 mg/d for patients in Japan) administered in divided doses three times per day (TID) with food. Initial pirfenidone treatment should be titrated over 14 days, as tolerated, to the full dose of 9 capsules per day (three capsules TID), as follows:

- Days 1–7: one capsule TID
- Days 8–14: two capsules TID
- Day 15 and continuing: three capsules TID (maximum of 9 capsules daily)

Each dose should be taken with food, at approximately the same times each day. Patients will remain on a stable maintenance dose for the duration of the study period unless the dose is reduced to manage an AE. All doses of pirfenidone are to be taken with food to reduce the likelihood of gastrointestinal symptoms. The dose titration period of 14 days at the initiation of treatment is designed to maximize tolerability. Exposure to sunlight (including sunlamps and tanning beds) should be avoided to minimize the possibility of photosensitivity reactions or rash. Patients should be instructed to use sunscreens that have a sun protection factor (SPF) of 50 or higher as well as protection against ultraviolet A (UV-A) and ultraviolet B (UV-B) radiation. Guidelines for dosage modification and treatment interruption or discontinuation are provided in Section 5.1.4. For patients treated with PIRESPA (limited to Japan), dose titration and management of

adverse effects should be based upon guidance in the marketed product label including a maximum recommended dose ≤ 1800 mg/d (Costabel et al. 2014).

If a patient experiences significant side effects, treatment of symptoms and/or temporary dose modifications should be considered. The decision to modify pirfenidone dosing is ultimately the responsibility of the investigator; however, occasional day-to-day variability in dosing due to patient initiative and preference is expected to occur.

Patients who enter the pirfenidone titration run-in period will be monitored for a minimum of 4 weeks and up to 6 weeks after screening and prior to randomization, to allow for dose modifications due to tolerability issues and to limit the requirement for dose adjustment during the 52-week study period.

Any overdose or incorrect administration of pirfenidone should be noted on the pirfenidone administration eCRF. Adverse events associated with either an overdose or incorrect administration of pirfenidone should be recorded on the Adverse Event eCRF.

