4.5.10 Pirfenidone Background Therapy (Cohort B)

IPF background therapy in Cohort B is pirfenidone. Pirfenidone licensed as ESBRIET or PIRESPA may be locally sourced for patients with access through their healthcare provider until it is provided by the Sponsor as IMP through the IxRS system. Patients consenting for Cohort B who are currently on a stable dose of pirfenidone (licensed as ESBRIET or PIRESPA) ≤ 2403 mg/d for ≥ 4 weeks will start the standard screening period of 28 days (± 14 days). Those patients who meet all eligibility criteria will then be randomized 1:1 to double blind treatment with SC lebrikizumab 250 mg or placebo every 4 weeks. Patients consenting to Cohort B who are not treated with pirfenidone at the time of screening will complete all screening assessments prior to initiating the pirfenidone titration run-in period. The Sponsor will provide background pirfenidone IMP to all patients who meet eligibility criteria within the 28-day (± 14 days) screening window. Pirfenidone titration and optimal patient dose will be determined during the 4–6 weeks “run-in” period to establish pirfenidone tolerability. A minimum period of 4 weeks from the first dose of pirfenidone will be required prior to randomization. Dose titration will

proceed based upon pirfenidone label guidance (see Section 4.3.4). If a patient experiences significant side effects, treatment of symptoms and/or temporary dose modifications should be considered (Costabel et al. 2014). The decision to modify pirfenidone dosing is ultimately the responsibility of the investigator; however, occasional day-to-day variability in dosing due to patient initiative and preference is expected to occur. Guidelines for dosage modification and treatment interruption or discontinuation are provided in Section 5.1.4. For patients treated with PIRESPA (limited to Japan), dose titration and management of adverse effects should be based upon guidance in the marketed product label, including a maximum recommended dose ≤ 1800 mg/d. Patients who fail to tolerate pirfenidone will be run-in failed and will not be randomized to this study.

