3. STUDY CONDUCT

3.1 RANDOMIZATION

Patients were randomized to the treatment arms through the interactive voice/Web-based response system (IxRS). After written informed consent is obtained, patients received a screening number, which was assigned by the IxRS. Following completion of the screening period and after all patient eligibility requirements were confirmed on Day 1, patients were to be assigned an identification number (a different number from the screening number) and randomized in a 1:1 ratio to one of two treatment arms for the 52-week placebo-controlled study period:

- **Cohort A** - lebrikizumab 250 mg SC or placebo SC every 4 weeks
- **Cohort B** - lebrikizumab 250 mg SC every 4 weeks and pirfenidone \leq 2403 mg/d or placebo SC every 4 weeks and pirfenidone \leq 2403 mg/d

Patients were to be randomized on the same day that treatment was to be initiated (Day 1/Visit 2).

Dynamic hierarchical randomization was performed centrally and stratified by the following factors:

- **Cohort A:** region (United States, Europe/Canada, other), lung function (FVC < 50%, 50% to 75%, > 75% predicted), and serum periostin concentration (< 50 ng/mL, ≥ 50 ng/mL)
- **Cohort B:** region (United States, Europe/Canada, other), lung function (FVC < 50%, 50% to 75%, > 75% predicted), and serum periostin concentration (< 50 ng/mL, ≥ 50 ng/mL). Although in the protocol amendment version 6 (2 December 2015) the region strata was to be replaced by prior perfenidone exposure but due to faster than anticipated accrual and logistic challenges this change was not implemented.

During the placebo-controlled study period and the open-label lebrikizumab treatment period, IxRS assigned study treatment kits for patients in Cohort A. During the placebo-controlled study period, IxRS will assign study treatment kits and pirfenidone treatment kits for patients in Cohort B. At each dosing visit during the placebo-controlled period, study and/or pirfenidone treatment kits will be distributed for administration. The placebo and active kits are filled and packaged to look identical. Patient randomization and treatment kit assignments will be verified on an ongoing basis by an external and independent statistical coordinating center to ensure that randomization and kit assignments are conducted correctly by IxRS.

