4.4.2 Primary Efficacy Endpoint

The primary endpoint is annualized rate of decrease in percentage of predicted FVC through Week 52, which will be compared across treatment arms with use of a random slope model on observed cases at a 0.05 two-sided significance level.

The statistical model is as follows:

$$FVC_{ijk} = (\beta_0 + \beta_{0k}) + (\alpha_i * \beta_1 + \beta_{1k}) * t_k + \eta_k + \epsilon_{ijk}$$

where FVC_{ijk} is the predicted FVC for kth patient at visit j in treatment group i; β_0 is the intercept; α_i and β_1 is the interaction term of the treatment effect ($i = \text{lebri or placebo}$) and the slope; t_k is assessment time (continuous in year) for patient k; η_k is the effect of baseline lung function (defined as $FVC < 50\%$ vs. 50% to 75% vs. $> 75\%$ predicted) for the kth patient; β_{0k} and β_{1k} are the random components for intercept and slope; ϵ_{ijk} is the random error for kth patient at time j; β_{0k} , β_{1k} , and ϵ_{ijk} are assumed to be independent and normally distributed with mean 0 and variance of σ_0^2 , σ_1^2 , and σ_ϵ^2 respectively.

Of note, because of a relatively large number of strata defined by the randomization stratification factors, the analysis will be adjusted for baseline lung function only because baseline FVC may impact the clinical disease course.

From the model, least squares means for the annualized rate of decrease in each treatment arm and the difference between the two treatment arms will be provided with

95% CIs. The model implicitly imputes missing data based on an individual's estimated rate of worsening of lung function prior to study visit discontinuation (i.e., assuming missing at random).

There are several different approaches to summarizing the treatment effect which are ways of understanding the results rather than independent endpoints. For summarizing treatment effect the following will be provided but not considered as separate endpoints or hypotheses.

- Change from baseline to landmark visit time expressed as absolute and relative difference
- Difference in annual rate of decrease expressed as absolute and relative difference
- Categorical absolute change from baseline to each visit time with categories of decrease of $\geq 10\%$ or death before the visit, decrease of 10% to $>0\%$, stability or improvement of change $\geq 0\%$

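### Cohort B pools new and established pirfenidone users, and the primary slope model does not account for prior exposure although stratification by it was once planned

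*Combined protocol and SAP*

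**What the plan says.** **Two entry routes.** Protocol 4.5.10 sends patients on a stable pirfenidone dose for at least 4 weeks straight into a screening period of 28 ± 14 days. Patients not on pirfenidone complete screening and then enter a titration run-in. Protocol 4.3.4 says of them: "Patients who enter the pirfenidone titration run-in period will be monitored for a minimum of 4 weeks and up to 6 weeks after screening". The same section sets a 14-day titration, with full dose from Day 15.

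**The 4-week requirement.** It is worded differently in several places:
- Protocol 4.1.1: "Cohort B: Tolerated dose of pirfenidone ≤ 2403 mg/QD for ≥ 4 weeks required prior to randomization".
- Protocol 3.2.3: "A minimum of 4 weeks of exposure to pirfenidone is required prior to randomization, anticipating 52 weeks of background therapy".
- Protocol 4.5.10: "A minimum period of 4 weeks from the first dose of pirfenidone will be required prior to randomization".
- Protocol 4.5.17.1: a 4-week minimum may be needed to establish tolerability.

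**Randomization.** Cohort B is stratified by region, lung function and periostin (Protocol 4.2, SAP 3.1). SAP 3.1 records that Amendment 6 would have replaced region by prior pirfenidone exposure, but "due to faster than anticipated accrual and logistic challenges this change was not implemented". The Version 7 amendment rationale adds that the randomization system could not be changed before enrollment finished.

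**Analysis.** For the primary slope model, SAP 4.4.2 states that "the analysis will be adjusted for baseline lung function only". The log-rank test and Cox model (SAP 4.4.3) are stratified by the same factor alone. Prior exposure (0, < 1 year, ≥ 1 year) is a Cohort B subgroup in SAP 4.4.6, Table 1, examined through its interaction with study drug in the MMRM for Week 52 change.

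**The concern.** On Day 1 some patients are a few weeks into pirfenidone and others have taken it for more than a year. If the two groups decline at different rates over the following 52 weeks, exposure is prognostic for the primary endpoint. The sponsor evidently thought it might be, since it tried to make exposure a stratification factor. The reasons given for not doing so are operational, not scientific.

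Once balance by design was lost, the usual substitute is adjustment in the analysis. The plan has none. The Table 1 subgroup asks whether the treatment effect differs by exposure, in the sensitivity model. It does not correct the primary slope contrast for a chance difference between arms in the share of new starters. At stake is a modest shift in the Cohort B estimate and a little precision.

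**Working it through.** **Inputs from the documents.** 165 per arm, target difference 2.5 points/year (4.1 to 1.6), SD 8, two-sided 5% (SAP 2.3); titration 14 days, run-in 28 to 42 days, capsules of 267 mg (Protocol 4.3.2, 4.3.4, 4.5.10).

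**Assumed inputs.** The documents give neither the share of new starters, *p*, nor the gap in annual decline between new and established users, *g*. I take *p* = 0.10 to 0.50 and *g* = 1 to 3.1 points/year. The upper value is the SAP's planning contrast between no pirfenidone and pirfenidone, 7.2 − 4.1 = 3.1. It is probably too high here, because both groups take pirfenidone during the 52 weeks. Imbalance is computed as under simple randomization.

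**1. The plan's own figure.** SE of the difference = 8 × √(2/165) = 0.88. Power is 0.810 by the normal approximation and 0.808 by the t-test, which agrees with the stated 80%.

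**2. Time on pirfenidone at Day 1.** New starters after titration: 28 − 14 = 14 days; 35 − 14 = 21 days; 42 − 14 = 28 days. Established users, if their 4 stable weeks precede screening: at least 28 + 14 = 42 days.

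**3. Chance imbalance.** SD of the between-arm difference in share = √(2p(1 − p)/165). The unfavourable draw is 1.96 times that, and the shift in the slope difference is the imbalance times *g*.

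| *p* | 95% imbalance (percentage points) | shift, *g* = 1 | shift, *g* = 2 | shift, *g* = 3.1 |
|---|---|---|---|---|
| 0.10 | 6.5 | 0.065 | 0.129 | 0.201 |
| 0.25 | 9.3 | 0.093 | 0.187 | 0.290 |
| 0.50 | 10.8 | 0.108 | 0.216 | 0.334 |

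The range is 0.065/0.88 = 0.07 to 0.334/0.88 = 0.38 standard errors, or 0.065/2.5 = 3% to 0.334/2.5 = 13% of the target difference.

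**4. Precision.** Treating 8 as the SD within an exposure group, the pooled SD = √(64 + p(1 − p)g²). This runs from 8.006 (*p* = 0.10, *g* = 1) to 8.149 (*p* = 0.50, *g* = 3.1). T-test power goes from 0.807 to 0.794, against 0.808 without mixing, so the largest loss is 0.808 − 0.794 = 0.014. The number per arm for 80% power (normal approximation) goes from 161 to 167, against 165 planned.

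**5. Which model term matters.** In the SAP 4.4.2 equation, lung function enters as an additive effect that does not multiply time. An exposure term added in the same way would move intercepts only. To protect the slope contrast, exposure must also interact with time.

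**The case against.** The best defence is that the mixing is deliberate and harmless to validity. Both routes are openly described, allocation is 1:1 within the cohort, and chance imbalance in an unstratified factor is already covered by the standard error and the 5% test. The random slope per patient allows for differing rates of decline. The SAP explains the single covariate by the large number of strata, and Table 1 does examine exposure. All of this stands. It shows that the primary test is valid, but it does not show that a known, already collected, possibly prognostic factor should stay out of the slope model.

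Stronger readings that the documents do not support:
- **That the run-in route breaches the inclusion criterion.** A reader might infer this from 4.1.1 by taking a tolerated dose to mean the maintenance dose. But the titration doses (3 × 267 = 801 and 6 × 267 = 1602 mg/d) also lie below 2403 mg/d, and 3.2.3 and 4.5.10 count exposure or time from first dose. On that reading every permitted run-in complies; on the other, only the 42-day maximum does. This is loose wording, not a demonstrated breach.
- **That new starters have only 2 weeks after titration.** That is the minimum; the range is 2 to 4 weeks.
- **That pooling biases the comparison.** Randomization prevents that.
- **That the shift could be much larger.** A gap of, say, 4 points/year would exceed the SAP's own 3.1-point contrast between no pirfenidone and pirfenidone.
- **That the adverse event comparison is distorted.** Protocol 5.1.4 does place most early pirfenidone intolerance in the first months. However, patients who cannot tolerate it fail the run-in, and the documents give no figures from which a between-arm effect could be calculated.

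**Conclusion.** The point holds as a small, inexpensive improvement. Prior pirfenidone exposure was dropped from stratification for operational reasons, and no adjustment in the primary analysis took its place. The cost is chance imbalance worth roughly 0.1-0.3 points/year in an unfavourable draw (under 0.4 SE, against a 2.5-point target) and at most about 1.5 points of power. Typical draws would be milder. These sizes depend on the assumed share of new starters and slope gap and on the simple-randomization approximation. The planned analysis is valid without the change.

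**What to change.** Before Cohort B is unblinded, add the SAP Table 1 exposure category (0, < 1 year, ≥ 1 year) and its interaction with time to the Cohort B primary slope model. Failing that, pre-specify the same model as a supportive slope analysis. The categories are already defined and the subgroup analysis already needs the data, so the cost is a few extra model terms and an SAP amendment.

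Separately, Protocol 3.2.3, 4.1.1, 4.3.4, 4.5.10 and 4.5.17.1 should be reconciled on what the 4-week pirfenidone requirement counts from. I take no position on which rule is right.
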